9.3.2 Additional Analyses Related to Primary Efficacy Outcome

For each of the following populations, the proportion of patients achieving treatment success will be summarized for each treatment group and diabetic type, and compared using the same method as for the primary efficacy analysis specified above.

- ARS
- Patients in EAS population with nadir glucose <50 mg/dL on both treatment visits.

Among patients who achieve treatment success, the proportion of patients achieving (1) an increase in glucose to \geq 70 mg/dL, or (2) an increase of \geq 20 mg/dL from nadir, or (3) an increase in glucose to \geq 70 mg/dL and an increase of \geq 20 mg/dL from nadir will be summarized for each treatment group and compared using the same method as for the primary efficacy analysis specified above for all 3 populations (ie, EAS, ARS, and EAS with nadir \leq 50mg/dL on both treatment visits).

As an additional sensitivity analysis, in the EAS population, the primary efficacy outcome will be assessed by comparing the upper limit of a 2-sided 95% CI on the difference in proportions obtained from a Poisson regression model using the binary primary outcome, accounting for the correlation due to the cross-over design using a generalized estimating equation. The model will include adjustments for nadir glucose level and treatment period.

Below is the example SAS code computing the treatment difference in proportion of patients achieving treatment success and 95% CI using the Poisson regression model:

```
proc genmod data=a;
class visit treatment patient;
model success = treatment visit nadir / dist=poisson link=identity;
repeated subject=patient / type=un;
estimate 'success' treatment 1 -1;
lsmeans treatment / diff cl om;
run;
```

The time from study drug administration to achieve treatment success will be summarized. A Kaplan-Meier (KM) analysis will be used to analyze the time from study drug administration to achieve treatment success. If both components of the treatment success (ie, an increase in glucose to \geq 70 mg/dL and an increase of \geq 20 mg/dL), are achieved for a patient, the earlier time point will be used. If a patient receives an external measure to raise glucose at any point, right censoring will be used. A treatment group comparison of the time to achieve treatment success

Final, 01 Feb 2018 Page 11 of 26

will be performed using Cox proportional hazard models accounting for the correlation due to the crossover design, adjusted for baseline glucose value and treatment period. Due to the discrete time data (5-, 10-, or 30-minute intervals), the exact method will be used. This method averages the Cox proportional hazards likelihood over all possible orderings of tied event times.

In addition, time to achieving either an increase in glucose to \geq 70 mg/dL or an increase of \geq 20 mg/dL from nadir will also be analyzed, separately, using the KM estimator of the survival function.

Below is the example SAS code creating KM life table and curve by treatment group:

```
proc lifetest data=b plots=(s) outsurv=kmtable;
time minutes*censor(1);
strata treatment;
run;
```

Below is the example SAS code using proportional hazard model:

```
proc phreg data=b covs(aggregate);
id patient;
class treatment visit;
model minutes*censor(1) = treatment visit nadir / ties=exact;
run;
```

For the time to event analysis, if a patient receives additional intervention treatment to raise glucose prior to achieving a glucose value ≥ 70 mg/dL or an increase of ≥ 20 mg/dL from nadir, the remaining time points will be considered as non-events (ie, glucose is not ≥ 70 mg/dL and does not increase ≥ 20 mg/dL from nadir).

The time to treatment success analysis will also be repeated in EAS patients with nadir glucose value <50 mg/dL.

A complete by-patient listing of primary efficacy data will be created.

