Three clinical trials using LY900018 have been completed in non-Japanese adults with T1DM and T2DM: Study IGBC, Study I8R-MC-IGBA (IGBA), and an actual use study (Study I8R-MC-B002 [B002]). Studies IGBC and IGBA demonstrated comparable safety and efficacy between 3 mg LY900018 and 1 mg injectable glucagon in reversing insulin-induced hypoglycemia in adult patients with T1DM only (Study IGBA) or patients with T2DM and T1DM (IGBC). Study B002 was an actual use study that evaluated the effectiveness of 3 mg LY900018 administered by a trained caregiver to patients with T1DM experiencing moderate to severe hypoglycemia in a real-world environment of work and home. Study B002 demonstrated that 96% of moderate to severe hypoglycemic events were resolved within 30 minutes. Finally, 2 trials were conducted in pediatric patients with T1DM: Study I8R-MC-IGBB (IGBB) and Study I8R-MC-B001 (B001). Studies IGBB and B001 demonstrated effectiveness in rescuing pediatric patients from hypoglycemia.

All adult diabetic patients in the 2 inpatient clinical trials (Studies IGBA and IGBC) underwent hypoglycemia induction through IV insulin under close clinical supervision and were administered either LY900018 or injectable glucagon.

Patients fully recovered from hypoglycemia without additional actions to increase glucose level. Specifically, in Study IGBC, at 30 minutes after glucagon dosing, 98.7% (74 out of 75 patients) of LY900018 and 100% (75 out of 75) of IMG-treated patients achieved treatment success (defined as an increase in PG to \geq 70 mg/dL or an increase of \geq 20 mg/dL from nadir). The nadir is defined as the minimum glucose measurement at the time of or within 10 minutes following glucagon administration. The LY900018-treated patient who did not meet the above criteria did achieve both PG \geq 70 mg/dL and an increase of \geq 20 mg/dL from nadir at 40 minutes after dosing. Furthermore, the mean time to treatment success in participants with nadir glucose <50 mg/dL were 16 minutes in the LY900018 treatment arm and 13 minutes in the IMG treatment arm, respectively (Rickels et al. 2016).

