7. SAMPLE SIZE JUSTIFICATION

Seventy five patients may be enrolled in order to have at least 66 patients (at least 30 patients with T1DM and T2DM, respectively) complete the study. For purposes of this study, a completer is defined as a patient who completes both periods with evaluable primary outcome. If patients discontinue from the study before completion of both periods with evaluable primary outcome for any reason, the patient may be replaced to ensure 66 patients complete the study. The replacement patients will be assigned the same treatment sequence as the patients to be replaced and will complete that treatment sequence in its entirety. Replacement should not occur beyond 75 patients enrolled, if it is expected to have at least 66 patients complete the study.

Assuming a non-inferiority margin (NIM) of 10%, a 98% treatment success rate for both treatment groups, and a within-patient correlation of zero, 66 completers will provide at least 90% power to show non-inferiority between LY900018 and IMG in treatment success from insulin-induced hypoglycemia with one-sided alpha level of 0.025 based on the Chi-square test.

The proposed NIM of 10% has been chosen based on the previously completed Phase 3 study (Rickels et al. 2016)³.

Final, 01 Feb 2018 Page 8 of 26

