9.3 Efficacy Assessment

9.3.1 Primary Efficacy Analysis

The primary outcome is the treatment success, which is defined as an increase in plasma glucose (PG) to \geq 70 mg/dL or an increase of \geq 20 mg/dL from PG nadir within 30 minutes after receiving glucagon, without receiving additional actions to increase the PG concentration. The nadir is defined as the minimum PG concentration at the time of or within 10 minutes following glucagon administration.

The primary analysis will be a treatment group comparison of the primary outcome in the EAS. The percentage of patients achieving treatment success in each treatment group and the difference in percentages will be computed. A 2-sided 95% CI will be obtained from the 1-sample mean of the paired differences in primary outcome (1 = outcome observed; 0 = outcome not observed) across 2 treatment visits. Noninferiority of nasal glucagon (NG) will be declared if the upper limit of a 2-sided 95% CI constructed on the difference in percentages (IMG minus NG) is less than the noninferiority margin of 10%. Specifically, for each patient, the paired difference of treatment success between IMG and NG will be calculated and PROC TTEST will be used to create the 95% CI of the mean difference.

Primary efficacy analysis will only include patients who complete both treatment visits with evaluable primary outcome. The analysis will be performed separately for each diabetes type. The following will be considered as nonevaluable primary efficacy outcome and excluded from the analysis related to primary efficacy outcome:

Final, 01 Feb 2018 Page 10 of 26

- Patients with at least 1 treatment visit in which the nadir PG is \geq 70 mg/dL;
- Patients receiving an external measure to raise PG concentration either before glucagon administration or within the first 10 minutes after glucagon administration.

Plasma glucose concentrations assessed through a central laboratory will be used to assess treatment success.

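### SAP 9.3.2 compares the components of success only among successes, and the paired method has no rule for a patient who succeeded on one treatment only

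*SAP*

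**What the plan says.** Success is met by either of two glucose criteria within 30 minutes, provided nothing else was given to raise glucose (SAP 9.3.1). SAP 9.3.2 then asks by which route success was reached: component (1) is at least 70 mg/dL, component (2) is a rise of at least 20 mg/dL from nadir, and component (3) is both. The set analysed is given as "Among patients who achieve treatment success, the proportion of patients achieving" each component. The proportions are to be "compared using the same method as for the primary efficacy analysis specified above for all 3 populations": the EAS, the ARS, and EAS patients with a low nadir on both visits.

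The primary method is defined in SAP 9.3.1: "for each patient, the paired difference of treatment success between IMG and NG will be calculated and PROC TTEST will be used" to form the confidence interval. It needs one 0/1 value per treatment from each patient.

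The SAP does not say whether the restriction means success on both visits, on at least one visit, or on the visit concerned. It gives no rule for a patient who succeeded on one treatment only.

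**The concern.** Success belongs to a visit, and each patient has two visits. Restricting the comparison to successes therefore causes two problems.

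- **It conditions on the outcome.** The denominator is fixed after randomisation by the result under study. If each treatment has its own denominator, a treatment with more failures can show the same component rate as its comparator, because its failures have left the denominator.
- **The pairing breaks.** A patient with one success and one failure belongs to the success group for one treatment and not for the other. The SAP does not say whether that patient is dropped, kept with a 0, or counted on one side only.

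At stake is the only between-treatment contrast of component proportions that the SAP states. For the separate components, the time-to-event text names the Kaplan-Meier estimator; the Cox comparison is specified for time to treatment success. Without a rule, the choice falls to whoever programs the analysis of an open-label study, possibly after data have been seen.

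**Working it through.** **Inputs.** SAP section 7: "Assuming a non-inferiority margin (NIM) of 10%, a 98% treatment success rate for both treatment groups, and a within-patient correlation of zero". The same section plans for 66 completers, claims power of 90% or more, and sets a one-sided alpha of 0.025. Protocol 3.2, earlier study: "98.7% (74 out of 75 patients) of LY900018 and 100% (75 out of 75) of IMG-treated patients achieved treatment success".

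**1. The plan's own figure.** With the unpooled normal formula, SE = √(2 × 0.98 × 0.02 / 66) = 0.0244, and power = Φ(0.10/0.0244 − 1.96) = 98.4%. Exact enumeration of the planned paired t interval, with probability 0.98 × 0.02 = 0.0196 of discordance in each direction and success declared when the upper limit is below 10%, gives 96.3%. Both meet the stated lower bound of 90%. A constrained-null normal approximation gives 80.0%, but that is not the planned interval. None of this bears on the component comparison.

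**2. How many patients lack a defined difference.**

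| Quantity | Formula | n = 66 |
|---|---|---|
| Success on one treatment only | n × 2 × 0.98 × 0.02 | 2.59 |
| Success on both | n × 0.98² | 63.4 |
| Failure on both | n × 0.02² | 0.03 |
| Chance of at least one one-sided success | 1 − (1 − 0.0392)ⁿ | 93% |

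For a single diabetes type with 30 completers, the last figure is 1 − 0.9608³⁰ = 70%.

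**3. What the readings give.** Illustration: 66 patients, 3 succeed on IMG only, 63 succeed on both, and (assumption) every success meets the component. With k patients favouring IMG and none favouring LY900018, d = k/n, v = (k − n·d²)/(n − 1), and the interval is d ± t × √(v/n).

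| Reading | n | IMG minus LY900018 (95% CI) |
|---|---|---|
| Success on both visits | 63 | 0.00 points, zero-width interval |
| Success on either visit, failed visit scored 0 | 66 | 3/66 = 4.55 points (−0.61 to 9.71) |
| Separate denominators | 66 and 63 | 66/66 − 63/63 = 0 points; no paired interval exists |
| All patients, failed visit scored 0 | 66 | 4.55 points (−0.61 to 9.71) |

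The second and fourth rows agree here because nobody failed on both treatments.

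With the earlier study's counts, and assuming the same 75 patients on both treatments, one patient succeeded on IMG only. The all-patient result is 1/75 = 1.33 points (−1.32 to 3.99). Restricted to success on both visits, it is 0.00 with a zero-width interval at n = 74.

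**4. Size of the conditioning with separate denominators.** Assume 95% of successes meet the component on each treatment, so the within-success difference is 0. The all-patient difference is 0.95 × (IMG success − LY900018 success):

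- LY900018 98%, IMG 98%: 0 points
- LY900018 94%, IMG 98%: 0.95 × 4 = 3.8 points
- LY900018 88%, IMG 98%: 0.95 × 10 = 9.5 points

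A purely hypothetical single-arm case: if LY900018 failed in 5 of 66 patients and 58 reached 70 mg/dL, the within-success rate is 58/61 = 95.1%, against 58/66 = 87.9% of all patients. The 5 and the 58 are not in the documents.

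**The case against.** The strongest reply is that this sentence only describes how success was reached and replaces no comparison of success. Most of that stands.

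- **A reader might infer that the plan hides failures.** It does not. Failures count in full in the primary EAS comparison, in the same comparison in the ARS and the low-nadir subset, and in the Poisson sensitivity analysis. Counts are reported with percentages for categorical data (SAP 9.1), so an all-patient rate can be rebuilt from the tables.
- **A reader might infer that the plan cannot show how often 70 mg/dL is reached.** SAP 9.3.2 also analyses time to each component separately by Kaplan-Meier, without limiting it to successes, and calls for a by-patient listing of the primary efficacy data. What is missing is a paired contrast: the Kaplan-Meier estimates do not use the pairing.
- **A reader might infer that every patient with one success and one failure is lost.** That is one of three readings. If success on either visit qualifies, the failed visit can score 0, as the primary coding already does, and only patients failing both visits leave (0.03 of 66 expected).
- **Patients discordant on success are not the only informative ones.** A patient who succeeds twice, once by reaching 70 mg/dL and once only by the 20 mg/dL rise, is informative for component (1) and stays in under every reading. The zero-width intervals above come from assuming that every success meets the component.

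The reply does not supply the missing rule, and it does not justify a between-treatment comparison in a set defined by the outcome.

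**Conclusion.** The point holds as a defect in one supportive comparison. The restriction to successes is explicit, it conditions on the outcome, and the paired difference is undefined for a patient with a single success.

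At the SAP's assumptions this concerns about 2.6 of 66 patients; with 3 such patients all favouring IMG, the estimate moves between 0.00 and 4.55 points according to the reading. That range assumes every success meets the component. The larger gaps (up to 9.5 points) require success rates well apart, which neither the planning assumption nor the earlier study suggests.

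The primary non-inferiority test, the sample size, the overall success comparisons and the component Kaplan-Meier analyses are unaffected. The documents do not support reading this as a threat to the trial's conclusion. Severity is low: worth correcting because it is cheap.

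**What to change.** Replace the restriction in SAP 9.3.2 with one sentence to this effect: in each of the three populations, all its patients form the denominator for components (1), (2) and (3); a component is met if reached within 30 minutes without additional actions to raise glucose; a failed visit scores 0; and the paired method of 9.3.1 is applied to every patient. Keep the breakdown among successes as counts and percentages, without a between-treatment interval.

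In the ARS, a patient with no outcome at one visit should be handled by whatever rule the overall success comparison in that set uses; this change does not settle that rule.

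The same edit can align the nadir cut-off, written as below 50 mg/dL in the list of populations and as at or below 50 mg/dL in the component sentence.

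The cost is one SAP sentence and a changed denominator in the programs. No new data and no change to the sample size are needed.

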8. DEFINITION OF ANALYSIS POPULATIONS

Five patient populations are defined for the analysis of this study:

- 1. All Entered Set Population (AES): All patients who sign inform consent and enter in this study
- 2. All Randomized Set Population (ARS): All patients who are randomized to study treatments
- 3. Full Analysis Set Population (FAS): All randomized patients who receive at least 1 dose of study drug
- 4. Efficacy Analysis Set Population (EAS): Patients in the FAS and have evaluable primary efficacy outcome
- 5. PK/PD Population: Patients in the FAS and have evaluable PK/PD.

Unless otherwise specified, efficacy analyses related to primary efficacy outcome will be conducted on data from EAS; other efficacy analyses and all safety analyses will be conducted on data from FAS; PK/PD analyses will be conducted on data from PK/PD population.

All protocol deviations that occur during the study will be considered for their severity/impact and will be taken into consideration when subjects are assigned to analysis populations.

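### SAP 9.3.2 gives two unreconciled rules for rescued patients in the time-to-success analysis and no censoring time

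*SAP*

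**What the plan says.** SAP 9.3.2 plans Kaplan-Meier curves and a Cox model for time from dosing to treatment success. It addresses rescue twice.

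- First rule: "If a patient receives an external measure to raise glucose at any point, right censoring will be used". No censoring time is given, and the trigger is not limited to rescue before success.
- Second rule, after the example code: "if a patient receives additional intervention treatment to raise glucose prior to achieving a glucose value" of at least 70 mg/dL or a rise of at least 20 mg/dL from nadir, then "the remaining time points will be considered as non-events".

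The Cox code, "model minutes*censor(1) = treatment visit nadir / ties=exact", takes one time and one flag per record. It does not show what `minutes` holds for a rescued patient.

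Three other statements bear on the point. SAP 9.3.1 defines success as reached "without receiving additional actions to increase the PG concentration". The same section makes some patients non-evaluable: "Patients receiving an external measure to raise PG concentration either before glucagon administration or within the first 10 minutes after glucagon administration". SAP section 8 says that "efficacy analyses related to primary efficacy outcome will be conducted on data from EAS", so these very early rescues do not enter. On the time scale, SAP 9.3.2 says: "Due to the discrete time data (5-, 10-, or 30-minute intervals), the exact method will be used". No analysis horizon is stated.

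**The concern.** A programmer could build either of two datasets from this text. In one, a patient rescued before success leaves the risk set at the rescue time. In the other, the same patient stays at risk, never has the event, and is censored at the end of follow-up.

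The first dataset does not fit the endpoint. Kaplan-Meier treats a censored patient as having the same later chance of success as those still at risk. A patient rescued before success has already failed by the definition in SAP 9.3.1, and Protocol 9.2.4 places post-dose IV glucose under insufficient response to glucagon. Censoring at rescue would therefore be informative and would tend to raise the success curve.

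The triggers also differ. Taken literally, the first rule reaches a patient who succeeded and was rescued later, and that recorded success could be turned into a censored record. The study is open-label, so the rule should be fixed before anyone knows who was rescued.

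**Working it through.** **The plan's own figures.** The documents give no figure for this analysis. The nearest is the power of at least 90% for the primary comparison (SAP section 7). It reproduces as a lower bound: SE = √(2 × 0.98 × 0.02 / 66) = 0.0244, and Φ(0.10/0.0244 − 1.96) = 98.4%. An exact calculation for the planned paired t-interval at zero correlation gave 96.3%. Neither depends on the rule at issue.

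**Inputs.** From the documents: 66 completers and 98% success (SAP section 7); plasma glucose samples every 5 min to 30 min, every 10 min to 60 min, then at 90, 120 and 240 min (Protocol section 2); glucose-threshold rescue at 30 and 45 min, with earlier rescue possible on clinical grounds (Protocol 9.2.4). Assumed: the rescue times and the success times.

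**Step 1: one worked case.** Take 66 patients, 3 of them rescued at 15 min. The other 63 succeed as follows: 9 at 10 min, 28 at 15, 17 at 20, 6 at 25 and 3 at 30.

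- Kept as non-events: success is (events so far)/66. At 25 min it is 60/66 = 90.9%; at 30 min it is 63/66 = 95.5%.
- Censored at 15 min: S(15) = (57/66)(29/57) = 29/66. The 3 leave, so 26 remain at risk. S(25) = (29/66)(9/26)(3/9) = 0.0507, so success is 94.9%. At 30 min the last 3 at risk succeed, so S = 0 and success is 100%.

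**Step 2: by number rescued**, with all other patients succeeding by 30 min and rescue at 15 or 20 min:

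| Rescued of 66 | Kept as non-event | Censored at rescue | Difference (points) |
|---|---|---|---|
| 1 | 65/66 = 98.5% | 100% | 1.5 |
| 2 | 64/66 = 97.0% | 100% | 3.0 |
| 3 | 63/66 = 95.5% | 100% | 4.5 |

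The ceiling is (number rescued)/66, because censoring can at most pass each rescued patient's 1/66 to later successes.

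**Step 3: rescue at 30 min or later.**

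- If no success follows the rescue, the two rules give the same curve.
- If rescue is at 30 or 35 min and 2 other patients succeed at 40 min, nothing differs at 30 min (with 3 rescued, 61/66 = 92.4% under both). From 40 min, censoring gives 100%, against 98.5%, 97.0% and 95.5% for 1, 2 and 3 rescued.
- Late success is possible: in the earlier Phase 3 study, the one nasal-glucagon failure met both criteria at 40 min (Protocol 3.2).

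**Step 4: how many failures to expect.** At 98% success, 66 × 0.02 = 1.32 failures per treatment. P(at least 1) = 1 − 0.98^66 = 74%; P(at least 3) = 15%. Not every failure need be rescued.

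**Step 5: rescue after success.** A patient with a nadir of 34 mg/dL who reaches 54 has met the 20 mg/dL criterion but is still below the 55 mg/dL threshold at which Protocol 9.2.4 allows IV glucose at 30 min. If such a patient were recorded as censored at 35 min instead of as a success at, say, 20 min, the 30-min estimate would fall by 1/66 = 1.5 points. This error runs the other way.

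**Step 6: Cox model.** This is an illustration only: two arms, assumed success times, Efron ties and no clustering, whereas the plan uses exact ties and patient-clustered variance. Hazard ratios are nasal/IM.

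| Rescues (nasal, IM) | Rescue time | Censored | Non-event |
|---|---|---|---|
| 1, 0 | 15 min | 0.605 | 0.590 |
| 2, 0 | 15 min | 0.591 | 0.562 |
| 3, 0 | 15 min | 0.577 | 0.537 |
| 3, 1 | 15 min | 0.590 | 0.600 |
| 3, 1 | 20 min | 0.584 | 0.600 |

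With 1 to 3 nasal rescues, no IM rescue, and rescue at 30 or 45 min, the two ratios are identical.

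**The case against.** The strongest reply is that the rules need not conflict. The first does not say that censoring happens at the rescue time. A patient who never has the event is, in this coding, a right-censored record, so the second rule can be read as spelling out the first: no event after rescue, censored at the end of follow-up. That stands, and it is why the point is put as two unreconciled rules and not as a contradiction. It does not close the gap. Censoring triggered by an event is ordinarily read as censoring at that event, the end of follow-up is not defined, and the triggers still differ.

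It is also fair to say that the illustrated rescues at 15 or 20 min are less likely than later ones. The glucose thresholds apply at 30 and 45 min, rescue in the first 10 min is excluded, and Protocol 3.2 reports 1 failure in 150 treatments in the earlier study, with recovery without additional action. That stands too, and it keeps the expected effect small.

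A reader might infer more than the documents support:

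- That failures are removed. They are not: a censored patient counts in the risk set until the censoring time.
- That the hazard ratio always moves toward the treatment with more rescues. In the illustration the shift is sometimes zero and sometimes reversed.
- That this is the only comparison of speed of recovery. SAP 9.5.2 compares time to maximal glucose between treatments, and SAP 9.5.3 compares glucose at each time point over 90 minutes.

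**Conclusion.** The point holds as a minor one. The text leaves the time and flag for a rescued patient open, and the ordinary reading of the first rule gives informative censoring at odds with the endpoint.

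The size is at most about 1.5 percentage points on the success curve per rescued patient of 66, and it arises only when other patients succeed after the rescue. SAP 9.3.2 repeats the analysis in patients with nadir below 50 mg/dL. That group's size is not given; if it were 20 to 33, the ceiling would be 1/20 = 5.0 to 1/33 = 3.0 points per rescued patient. All of these figures rest on assumed rescue and success times.

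It might be inferred that the trial's main conclusion is exposed. It is not. Time to success is an additional analysis and is not among the endpoints in Protocol section 4. The primary outcome already requires success without additional action, so the primary proportion, its confidence interval and the non-inferiority decision are the same under either rule.

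**What to change.** Replace the right-censoring sentence in SAP 9.3.2 with one rule that governs both the Kaplan-Meier and PHREG datasets:

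- A patient rescued before success stays in the risk set, has no event after rescue, and is censored at a stated analysis horizon.
- The horizon is named: either 30 minutes, which matches the success definition, or a stated last glucose time. The listed 5-, 10- and 30-minute intervals imply follow-up beyond 30 minutes. They do not cover the 120-minute step to the 240-minute sample, so the intended end cannot be read from the text.
- Rescue after success leaves the recorded success time unchanged.

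Define `minutes` and `censor` in those terms beside the example code. The cost is one short paragraph and one derivation rule, with no new data and no effect on sample size. SAP section 3 requires sign-off before the first dose, so the rule belongs in the text by then.
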